#### **1. ABBREVIATIONS**:

CF	Cystic fibrosis
EMA	European Medicines Agency
PASS	Post-authorisation safety study

# **3. STUDY SYNOPSIS**

Study Title	Prospective Case-Control Safety Study of Bronchitol (inhaled mannitol) in Patients with Cystic Fibrosis from the UK CF Registry
Protocol Version and Date	Version 1.0 - 18 th June 2012
Principal Investigator	[name] Royal Brompton Hospital London UK
Study Design	Observational cohort study
Rationale/Background	This post-authorisation safety study (PASS) is being conducted pursuant to an obligation imposed by the EMA as a condition of the granting of a marketing authorisation for Bronchitol (mannitol) to confirm the safety profile of Bronchitol, identify, characterise and/or quantify any emergent safety issues , and measure the effectiveness of agreed risk management strategies
Study Participants	Exposed: Adult (≥ 18years) patients in the CF registry database who are prescribed Bronchitol Unexposed: Non- treated patients matched for key characteristics with exposed patients)
Planned Sample Size	All Bronchitol-treated patients with evaluable data in the UK CF Registry during the 5-year study period
Planned Study Period	June 2012 – July 2017
Primary Objective(s)	To assess the rates of identified and potential risks of Bronchitol through a comparison of treated vs. non-treated patients
Secondary Objective(s)	
 
To compare the rates of identified and potential risks against background rates in the general CF population.
 
To assess the rate of identified and potential risks in the population below 18 years of age
 
To compare the effect on lung function in treated vs. non-treated patients
 
To compare the effect on CF exacerbations in treated vs. non-treated patients
 

Data Sources	Data will be obtained from the UK CF Trust Registry
Data Analysis	At each analysis time logistic regression models will estimate propensity scores for treated and untreated patients. Bronchitol- treated patients will be compared with untreated patients matched on key characteristics. Descriptive statistics will be used to describe the treated and untreated patient groups. Negative binomial models will be used to compare the number of adverse events between treated and untreated patients. Cox's proportional hazards models will be used to compare time to the first adverse event. Random effects linear models will be used to study changes in FEV 1 over time. Modelling will be performed with and without

	adjustment for potential confounders. For comparisons with the full population similar models will be used adjusting for propensity scores.
Milestones	Interim analysis will be performed 6 monthly for 3 years and then annually for 2 years, the final study report is expected in Q1 2018.

#### **4. RATIONALE AND BACKGROUND**

Bronchitol™, a spray dried mannitol, was recently granted Marketing Authorisation by the European Medicines Agency (EMA)for the treatment of CF in adults aged 18 years and above as an add on therapy to best standard of care. Safety data for Bronchitol from two large phase III studies with Bronchitol, is available for up 18 months, however long term safety data has not be collected for exposure beyond 18 months.

In an orphan disease, the exposure to a new product may take considerable time to establish a large post marketing safety experience. Pursuant to an obligation imposed by the EMA as a condition to the granting of the marketing authorisation, Pharmaxis are undertaking a post-authorisation safety study (PASS) to; confirm the safety profile of Bronchitol, identify, characterise and/or quantify any emergent safety issues, and measure the effectiveness of agreed risk management strategies.

Disease/outcome registries are important resources when seeking to collect data on drug exposure and/or other factors associated with a clinical condition. Exposure registries address populations exposed to medicinal products of interest to determine if a medicinal product has a special impact on this group of patients. Some exposure registries address exposures to medicinal products in specific populations. Patients may be followed over time and included in a cohort study to collect data on adverse events using standardised questionnaires. Simple cohort studies may measure incidence, but, without a comparison group, cannot evaluate any association between exposures and outcomes. Nonetheless, they may be useful for signal amplification particularly for rare outcomes. This type of registry may be very valuable when examining the safety of an orphan drug indicated for a specific condition. Notwithstanding some inherent limitations in registry studies, they do provide an appropriate base for surveillance studies.

The European CF community is close knit and meets and communicates regularly in order to develop a consensus on best practice. As such, management of CF in most EU countries is broadly uniform, with shared long term goals. This situation means that it is possible to undertake a registry study in a member state of the EU and extrapolate the results more broadly to the EU CF community. If significant differences in prescribing patterns are subsequently identified, the matching of patients by concomitant medication use should, in time, allow examination of specific sub-groups based on particular prescribing patterns that may be more favoured in a region.

The Cystic Fibrosis Trust in the UK currently has a well established and comprehensive patient registry. The UK CF Trust Registry represents one of the largest and most mature databases available in Europe and is broadly viewed as representative for the wider EU. Over 90 CF treatment centres in the UK contribute data to the registry and information is collected on more than 7,000 patients with CF annually.

The purpose of this study is to assess the rates of identified and potential risks of Bronchitol in CF through a comparison of Bronchitol-treated vs. non-treated patients in a matched cohort study from the CF registry over 5 year period. Safety analysis will be conducted and reported on a 6 monthly basis for the initial three year period and then annually for two years.

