#### 5. RESEARCH QUESTIONS AND OBJECTIVES

Primary Objective:

To assess the rates of identified and potential risk of Bronchitol in CF through a comparison of Bronchitol treated vs. non-treated patients in a cohort matched for key characteristics from the CF registry over a 1 to 5 year period. Safety analysis would be conducted on a 6 monthly basis for three years and then annually for two further years.

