#### 10. DATA ANALYSIS

This is a safety observational study, and therefore the focus is the safety endpoints (AEs of special interest).

At each analysis time a propensity score analysis will be performed. Here we will use logistic regression to estimate the probability of being treated with Bronchitol. This will generate a propensity score for each patient which will be used in subsequent analyses.

Full Analysis Population

All patients (treated and untreated) from CF Registry will be included in the analyses. For this population, we will include:

- Simple descriptive analyses (frequency and percentage) for AEs

- Negative Binomial regression for the count of events for each AE with adjustment for propensity scores.
- Cox regression for time to first event for each AE (Hazard Ratio), with adjustment for propensity scores.
- Matched Analysis Population

Analysis for the treated and matched untreated population will include:

- Descriptive analysis of the distribution of risk factors between the two groups of patients
- Simple descriptive analyses of AEs
- Negative Binomial regression for the count of events for each AE with and without any adjustment for potential confounders
- Negative Binomial regression assessing the interaction test between treatment and each important risk factor. Each risk factor will be tested one by one
- Subgroup analyses
  - Simple descriptive analyses and negative binomial regression (without any adjustment) for each AE for each subgroup. Subgroups will be defined a priori. Forest plots will be used to plot the Rate Ratios for all subgroups.

Cox regression will be used to study the time to first event for each AE. As for the negative binomial regression models these will be done both with and without adjustment for potential confounders.

Random effects linear models will be used to study changes in  $FEV_1$  over time. As with other regression models these will be performed with and without adjustment for potential confounders.

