#### 12. MANAGEMENT AND REPORTING OF ADVERSE EVENTS/ADVERSE REACTIONS

Adverse events will not be reported on an expedited basis for this study as it is an observational cohort study designed to collect long-term safety information using secondary data. All safety information will be assessed and submitted in interim analysis reports and will be submitted according to the schedule agreed as part of the post-authorisation commitment for this study. A full review of the safety information collected for the full study period will be presented in the final study report.

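### The rationale names exposure beyond 18 months as the gap in safety data, but no adverse-event analysis in the protocol gives an estimate by time since start of exposure

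*Protocol*

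**What the plan says.** Protocol section 4 describes safety data from two phase III studies lasting up to 18 months and adds that "long term safety data has not be collected for exposure beyond 18 months". It then gives the regulatory obligation behind the study: to "confirm the safety profile of Bronchitol, identify, characterise and/or quantify any emergent safety issues, and measure the effectiveness of agreed risk management strategies". Section 12 describes the study as "designed to collect long-term safety information using secondary data". The primary objective in section 5 compares treated with untreated patients "in a cohort matched for key characteristics from the CF registry over a 1 to 5 year period".

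Section 10 sets out the adverse-event analyses, apart from simple descriptive summaries:

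- Full population: "Negative Binomial regression for the count of events for each AE with adjustment for propensity scores", and "Cox regression for time to first event for each AE (Hazard Ratio), with adjustment for propensity scores".
- Matched population: "Negative Binomial regression for the count of events for each AE with and without any adjustment for potential confounders". In addition, "Cox regression will be used to study the time to first event for each AE", again with and without adjustment.
- Interaction tests of treatment with each important risk factor, and subgroups to be defined in advance. Neither the factors nor the subgroups are listed.

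The synopsis specifies proportional hazards models. Change over time is modelled only for FEV1, which is a secondary outcome and not an adverse event.

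**The concern.** Each adverse-event model, as described, compresses the whole of follow-up into one treatment effect. That effect mixes the first 18 months on drug, which the phase III studies already covered, with the later period, for which section 4 says there are no data. If a risk appears only with long use, the pooled ratio understates it.

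The first-event Cox model adds a further loss. A patient with an early event leaves the risk set and contributes nothing to the later comparison. Patients who start near the end of data collection also enter the average without being able to reach 18 months.

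At stake is whether the final report can say anything specific about use beyond 18 months, and whether a modest overall ratio would be read as long-term reassurance when part of it rests on short exposure.

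**Working it through.** The protocol gives no sample size, event count or power figure, so there is no stated number to reproduce. The check is of how far a late effect would be diluted.

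**Inputs from the protocol.** Data collection runs from 1 July 2012 to 30 June 2017, which is 5 years (section 17). The boundary is 18 months, or 1.5 years (section 4).

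**Assumptions.** Uptake and persistence are not given, so starts are taken as uniform over the 5 years, with constant stopping hazard h of 0, 0.25 or 0.5 per year (about 0%, 22% and 39% stopping per year, from 1 − e^(−h)). The baseline event rate is constant. Treated time counts only while on drug. The rate ratio is 1 up to 18 months and R = 2 afterwards.

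**Pooled rate ratio.** If s is the share of exposed person-time beyond 18 months, the pooled ratio is (1 − s) × 1 + s × R = 1 + s(R − 1).

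**Share s with uniform starts.**

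- No stopping: mean total time is 5/2 = 2.5 years. Mean late time is (3.5²/2)/5 = 1.225 years. So s = 1.225/2.5 = 0.490.
- With stopping: mean total time is (1/h)[1 − (1 − e^(−5h))/(5h)]. Mean late time is (1/(5h))[3.5e^(−1.5h) − (e^(−1.5h) − e^(−5h))/h].
  - h = 0.25: 0.642/1.717 = 0.374.
  - h = 0.5: 0.349/1.266 = 0.276.

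**All start on day one, none stop:** s = 3.5/5 = 0.70.

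| Scenario | s | Pooled ratio when R = 2 |
|---|---|---|
| All start on day one, none stop | 0.70 | 1.70 |
| Uniform starts, h = 0 | 0.490 | 1.49 |
| Uniform starts, h = 0.25 | 0.374 | 1.37 |
| Uniform starts, h = 0.5 | 0.276 | 1.28 |

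With uniform starts, 1.5/5 = 30% of starters cannot reach 18 months before data collection ends.

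**Cox model, first events (approximate).** The formula above does not apply to the Cox model. A rough average hazard ratio is exp(s_e × ln 2), where s_e is the share of first events, at the untreated rate, that fall beyond 18 months. With uniform starts and 0%, 20% or 40% stopping per year:

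- Baseline rate 0.05 per year: s_e = 0.466, 0.364, 0.255, so the hazard ratio is about 1.38, 1.29, 1.19.
- Baseline rate 0.5 per year: s_e = 0.276, 0.206, 0.139, so the hazard ratio is about 1.21, 1.15, 1.10.

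The commoner the event, the stronger the dilution, because early first events empty the late risk set.

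**Do the interim periods separate late exposure?** Section 17 lists 3 × 2 + 2 = 8 periods, all in calendar time. With uniform starts and 0%, 20% or 40% stopping per year, the share of exposed time beyond 18 months is zero in the first three periods and 67%, 55% or 40% in the last. Even the last period mixes new and long-term users.

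**The case against.** The strongest reply is that this is statistical analysis plan material. Only the protocol is at hand, and a separate plan may define time bands or list exposure duration among the subgroups or interaction factors. In addition, no objective in section 5 promises an estimate beyond 18 months, and section 9 gives the main purpose as estimating incidence with confidence intervals.

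Much of this stands, and it rules out several stronger readings that a reader might infer:

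- That the study exists because of the 18-month gap. Its stated reason is the broader regulatory obligation; the gap is part of the background.
- That every planned estimate averages over exposure. FEV1 is modelled over time, and the interim periods, if analysed separately, give a coarse calendar view.
- That a late risk would never be reported separately. That cannot be concluded while the subgroups and factors are unlisted and the analysis plan is unseen.
- That the pooled result is driven by the early months or would be null. In the base case 49% of exposed time is late, and a late doubling still pools above 1 in every scenario.
- That only first events are analysed. Event counts are already planned in both populations.

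The reply does not dispose of the mismatch. Section 10 is specific about models, populations, interactions and forest plots, so the omission is not merely a lack of detail. Its open slots concern patient risk factors. Exposure duration is not a characteristic that untreated patients have; it requires follow-up in both groups to be split from a shared index date. Grouping patients by the duration they reached would condition on persistence and survival, so it is no substitute.

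The data limits also count. Records are entered annually (section 7), and new infections and increased oral steroid use are dated only to the annual review (section 16). Fine bands, such as a cut at 6 months, would be unreliable for those outcomes. A single cut at 18 months is workable but approximate for them.

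**Conclusion.** The concern holds as a mismatch between the rationale and the analyses the protocol describes: section 4 identifies exposure beyond 18 months as the gap, and no adverse-event analysis shown gives an estimate for it. The consequence is attenuation. A doubling confined to the late period would appear as a rate ratio of about 1.28 to 1.49 with uniform starts and stopping hazards of 0.5 down to 0 per year, or about 1.70 if all start on day one and none stop. The first-event Cox ratio would be about 1.10 to 1.38, on a rough approximation.

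These sizes rest on assumed uptake, persistence, a constant baseline rate and treated time ending at discontinuation, none of which the protocol states. They do not show that a late risk would go undetected, and the documents give no ground for ranking a late-period estimate above the overall comparison. The change is worth making because it is cheap and addresses the gap the protocol itself names.

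**What to change.** In section 10, add for each adverse event:

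- Rates per person-year in treated and matched untreated patients, and the rate ratio with 95% CI, separately up to and beyond 18 months from index. Use the negative binomial counts already planned, with a person-time offset.
- A Cox model in which the treatment effect may differ before and after 18 months.
- The number of patients and person-years beyond 18 months, so the reader can see what the late estimate rests on.

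Keep the overall estimate as planned. Flag outcomes dated only by annual review as approximate in the split.

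The cost is wider intervals in each period and a little more analysis work on data already to be collected. Section 9 sets an estimation aim and no power target, so the split breaks no power commitment.

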#### 5. RESEARCH QUESTIONS AND OBJECTIVES

Primary Objective:

To assess the rates of identified and potential risk of Bronchitol in CF through a comparison of Bronchitol treated vs. non-treated patients in a cohort matched for key characteristics from the CF registry over a 1 to 5 year period. Safety analysis would be conducted on a 6 monthly basis for three years and then annually for two further years.

#### Secondary Objectives:

- To compare the rates of identified and potential risks against background rates in the general CF population.
- To assess the rate of identified and potential risks in the population below 18 years of age who may receive Bronchitol "off-label".
- To compare the effect on lung function measured by FEV1 (mL, % change and % predicted change) in Bronchitol treated vs. non-treated patients with CFin a matched cohort from the CF registry as part of an overall benefit/risk assessment.
- To compare the effect on CF exacerbations (using IV antibiotic use as a surrogate) in Bronchitol treated vs. non-treated patients in a matched cohort from the CF registry as part of an overall benefit/risk assessment.

# 6. RESEARCH METHODS

#### Study Population and Main Criteria for Inclusion:

Adult ( $\geq$  18 years) patients in the CF registry database who are prescribed Bronchitol. The unexposed group are untreated patients. These will be matched with treated patients on key characteristics.

At the time of the study starting, Bronchitol is only indicated for adult CF patients. Nevertheless, it may emerge that there are a significant number of paediatric and adolescent (6-17 years) patients who are prescribed Bronchitol "off-label". Furthermore, in time, an indication in children is also planned. If sufficient patient numbers make it feasible, a matched cohort of non-treated patients will be identified based on similar age, disease severity and concomitant medications (rhDNase, inhaled antibiotics, chronic antibiotics, presence of chronic Pseudomonas).

#### Duration of Study Treatment:

As this is an observational study, no intervention will be attempted and no attempt will be made to influence treatment decisions. The goal is to retrospectively determine whether the risk factors of interest differ between treated and untreated patients.

#### 7. STUDY DESIGN

This is an observational cohort study which aims to collect anonymised data on all subjects taking Bronchitol who contribute annual data to the UK CF Registry and matched, untreated subjects. Data from individual subjects is currently entered into the Registry database annually. Data on treated and untreated patients will be analysed on a regular basis (at six-month intervals for the initial three years and then annually).

#### 8. SETTING

The UK CF Trust Registry represents one of the largest and most mature databases available in Europe and is broadly viewed as representative for the wider EU. Over 90 CF treatment centres in the UK contribute data to the registry and information is collected on more than 7,000 patients with CF annually. Data for analyses for this study will be wholly derived from patients with cystic fibrosis who have evaluable data available within the UK CF Registry.

#### 9. STUDY SIZE

This is an observational cohort study with safety as the primary endpoint. Therefore, it is desirable to include as many patients as possible to observe the safety endpoint. As the CF Registry will be used as the source data, all patients aged 18 years and older who are recorded to be taking Bronchitol and who have evaluable data available for analysis in the CF Registry will be included in the study. Bronchitol patients will be matched with untreated patients; all matched data from the Registry will be included in the analysis.

The incidences of haemoptysis and bronchospasm were reported to be similar between patients who received Bronchitol versus untreated patients in the controlled clinical trials. With the limitation of the data source, it is not practical to design a superiority study with adequate power to test a small incidence difference. Therefore the main purpose of the study is to estimate the incidence of identified AEs and their confidence intervals based on all available data from the Registry.

#### 10. DATA ANALYSIS

This is a safety observational study, and therefore the focus is the safety endpoints (AEs of special interest).

At each analysis time a propensity score analysis will be performed. Here we will use logistic regression to estimate the probability of being treated with Bronchitol. This will generate a propensity score for each patient which will be used in subsequent analyses.

Full Analysis Population

All patients (treated and untreated) from CF Registry will be included in the analyses. For this population, we will include:

- Simple descriptive analyses (frequency and percentage) for AEs

- Negative Binomial regression for the count of events for each AE with adjustment for propensity scores.
- Cox regression for time to first event for each AE (Hazard Ratio), with adjustment for propensity scores.
- Matched Analysis Population

Analysis for the treated and matched untreated population will include:

- Descriptive analysis of the distribution of risk factors between the two groups of patients
- Simple descriptive analyses of AEs
- Negative Binomial regression for the count of events for each AE with and without any adjustment for potential confounders
- Negative Binomial regression assessing the interaction test between treatment and each important risk factor. Each risk factor will be tested one by one
- Subgroup analyses
  - Simple descriptive analyses and negative binomial regression (without any adjustment) for each AE for each subgroup. Subgroups will be defined a priori. Forest plots will be used to plot the Rate Ratios for all subgroups.

Cox regression will be used to study the time to first event for each AE. As for the negative binomial regression models these will be done both with and without adjustment for potential confounders.

Random effects linear models will be used to study changes in  $FEV_1$  over time. As with other regression models these will be performed with and without adjustment for potential confounders.

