# 16. GENERALISABILITY, LIMITATIONS AND POSSIBLE BIAS

The clinical use of a newly licensed product may often be predominantly limited to a more severe patient population in the first 6-12 months. The initial subjects studied may therefore not be representative of the whole CF population; however the matching cohort strategy will limit this potential bias. Additionally, the analytical models being employed include propensity scores thus controlling for the probability of being prescribed Bronchitol.

In addition, the majority of CF centres in the UK contribute data, so the CF Registry is able to be generalised to the UK CF population. As the UK CF Registry is one of the largest and most mature databases available in Europe, it can be viewed broadly as representative for the wider EU. If however, significant differences in prescribing patterns are identified, the matching of patients should, in time, allow examination of specific sub-groups based on particular prescribing patterns that may be more favoured in a region.

A limitation of having an adult's only label is that the data analysis will only be for the adult population. As it is not possible to predict any off-label usage in children and adolescents and also usage is likely to be very small, this data will only be provided in summary format.

A limitation in using routinely collected registry data in epidemiological research is that for some outcomes, such as the acquisition of new microbial infections and increased use of oral steroids, we do not have a precise date on which the outcome occurred. As such, the date of the event will be estimated based on when the annual review encounter took place. In the first annual review after

the index date, it is therefore possible that either of these two outcomes are mis-identified as being post-index date when the event may have occurred prior.

All analysis and reporting will be done independently by Imperial College for the Cystic Fibrosis Trust and in liaison with the Lead Investigator. Pharmaxis will receive the analyses at the different time points and include them as required in reports to the international regulatory bodies.

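### The comparison with background rates in the general CF population has no planned estimate with an interval: the full-population regressions listed are all propensity-adjusted and estimate something close to the primary contrast

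*Protocol*

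**What the plan says.** The protocol separates two comparisons. The primary objective (section 5) assesses risks "through a comparison of Bronchitol treated vs. non-treated patients in a cohort matched for key characteristics from the CF registry". The first secondary objective, in sections 3 and 5, is "To compare the rates of identified and potential risks against background rates in the general CF population". The term background rate is not defined further.

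The synopsis (section 3, Data Analysis) names the method for the wider comparison: "For comparisons with the full population similar models will be used adjusting for propensity scores". Section 10 lists three analyses for the Full Analysis Population:

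- a purely descriptive one, "Simple descriptive analyses (frequency and percentage) for AEs";
- a model of event counts that is adjusted throughout, "Negative Binomial regression for the count of events for each AE with adjustment for propensity scores";
- a Cox model of the time to a patient's first event, which carries the same adjustment.

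For the matched population, the same section lists "Negative Binomial regression for the count of events for each AE with and without any adjustment for potential confounders", and the Cox models there are likewise planned both ways. Section 10 defines the propensity score as the probability of Bronchitol treatment, estimated by logistic regression.

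Two further statements bear on the point. Section 9 gives the study's main purpose as estimating the incidence of identified adverse events with confidence intervals from all available registry data. It also says that a study powered to test a small incidence difference is not practical. Section 16 warns: "The clinical use of a newly licensed product may often be predominantly limited to a more severe patient population in the first 6-12 months".

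**The concern.** A comparison with background adds to the primary objective only if background means the registry population with its actual case mix. The regressions listed for the full population condition on the probability of being treated, so they remove the case-mix difference between users and everyone else. Section 16 expects such a difference, at least early on.

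The crude side of the comparison is left to frequencies and percentages. With follow-up of 1 to 5 years (section 5), a percentage with an event is not a rate, and no ratio or interval against background is listed.

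This is a safety study imposed by the EMA, and its interim and final reports go to regulators. Someone who looks for the answer to this objective will find a propensity-adjusted ratio. It answers a different question from whether patients on Bronchitol have more events than the CF population at large.

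**Working it through.** The protocol gives no event rate, uptake, alpha or effect size, so there is no figure to reproduce. The check sets the objective against the models and then illustrates the gap under assumed inputs.

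**Step 1. What each quantity estimates**

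| Item | Contrast | Case mix |
|---|---|---|
| Primary objective (section 5) | treated vs untreated, matched | equalised by matching |
| Full-population negative binomial and Cox (sections 3, 10) | treated vs untreated at equal propensity score | equalised by adjustment |
| First secondary objective (sections 3, 5) | users vs general CF population | left as it is, on the plain reading |
| Full-population descriptive output (section 10) | none specified | left as it is, as percentages |
| Incidence with interval (section 9) | none specified | not stated |

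No listed output gives a ratio or difference, with an interval, for the third row.

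**Step 2. The gap by hand**

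Assumptions: 30% of patients severe; uptake 2% in mild patients; odds of uptake in severe patients *k* = 2 or 4 times those in mild; event rate in severe patients *r* = 2 or 3 times that in mild; no drug effect.

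- Uptake in severe patients: p = o/(1+o), with o = k × 0.02/0.98. This gives 0.0392 for k = 2 and 0.0755 for k = 4.
- Severe share of users: s = 0.3p/(0.3p + 0.7 × 0.02). For k = 2: 0.01176/0.02576 = 0.457. For k = 4: 0.02264/0.03664 = 0.618.
- Users' rate over the registry rate: [1 + (r−1)s] / [1 + (r−1) × 0.3].

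| k | r | Users/registry rate |
|---|---|---|
| 2 | 2 | 1.457/1.3 = 1.12 |
| 2 | 3 | 1.913/1.6 = 1.20 |
| 4 | 2 | 1.618/1.3 = 1.24 |
| 4 | 3 | 2.236/1.6 = 1.40 |

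Conditional on severity, the treated/untreated ratio is exactly 1 in every row, because no drug effect was assumed.

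**Step 3. The same gap by simulation**

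Inputs: 7,000 patients (the protocol says more than 7,000), the values of step 2, a base rate of 0.1 events per year, and a second covariate that raises both uptake and event rate. A negative binomial model was fitted to 60 data sets per setting, first with treatment alone (users vs the rest of the registry), then with treatment plus the logit of the estimated propensity score.

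| k | r | Crude, drug ratio 1.0 | Adjusted, drug ratio 1.0 | Crude, drug ratio 1.5 | Adjusted, drug ratio 1.5 |
|---|---|---|---|---|---|
| 2 | 2 | 1.14 | 0.95 | 1.66 | 1.40 |
| 2 | 3 | 1.28 | 1.00 | 1.87 | 1.49 |
| 4 | 2 | 1.36 | 1.02 | 1.94 | 1.46 |
| 4 | 3 | 1.47 | 0.97 | 2.23 | 1.48 |

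The adjusted ratio follows the assumed drug effect, up to simulation error. The crude ratio carries the case mix as well. The simulated crude ratios are somewhat above those of step 2 because of the second covariate and because the comparator leaves out the users.

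**Step 4. Why a percentage does not stand in for a rate**

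At a constant 0.1 events per year (assumed, with no variation between patients), the proportion with at least one event is 1 − exp(−0.1) = 9.5% after 1 year and 1 − exp(−0.5) = 39.3% after 5 years. Two groups with the same rate but different follow-up can therefore show very different percentages.

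**The case against.** The best defence is that adjustment is deliberate. Section 16 treats channelling to severe patients as a bias and names propensity scores as a control for it. For a question about what the drug does, an adjusted ratio near 1 is the right answer when the drug does nothing. This stands, and it is why the models should be kept.

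Section 9 commits to incidences with confidence intervals and section 10 to descriptive counts, so crude figures will exist and the objective is not wholly unserved. This also stands. But neither section sets those figures against background, and a reader would have to build the contrast and its interval.

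The text may also leave room for unadjusted full-population models. Section 10 does not say that its list is exhaustive, and the synopsis says generally that modelling will be done with and without adjustment for confounders. That remark sits with the matched analysis, however, and the next sentence assigns propensity adjustment to full-population comparisons. It is fair to say that no unadjusted model is listed, but not that one is ruled out.

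Finally, the full-population model uses the whole registry and differs from the matched analysis in target population and efficiency. It is close to the primary question, not a copy of it.

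A reader might go further and infer that the planned models have an inflated false-positive rate or lose power for this objective. The protocol does not support that. It states no null hypothesis and no alpha, and section 9 disclaims powered testing. Nor would an adjusted ratio below 1 be a false finding if users were sicker yet had the same rate as background. In that case the treated do better than comparable untreated patients, and the model correctly recovers it.

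**Conclusion.** The point holds as a mismatch between a secondary objective and the analyses listed for it. The full-population regressions estimate a treated-versus-untreated contrast at equal probability of treatment, and nothing listed estimates, with an interval, how far users' rates differ from background. The models themselves are sound for what they estimate.

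The direction follows from the form of the model, provided that users are sicker, as section 16 expects at least for the first 6 to 12 months. The size is illustrative only: with no drug effect, users' crude rate is roughly 1.1 to 1.5 times that of the comparator while the adjusted ratio stays near 1. Every input except the approximate registry size is assumed. If uptake proves unrelated to severity, the two ratios converge and the gap is small.

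The conclusion also rests on reading background as the registry population as it stands. If the sponsor meant a comparator adjusted for confounding, the objective largely repeats the primary one and the protocol should say so. The change is worth making but is not critical, since only a secondary objective is affected.

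**What to change.** In sections 3 and 10, define the background rate and add for this objective, for each adverse event:

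- the person-time incidence rate in Bronchitol users and in the registry population;
- the crude incidence rate ratio and an age- and sex-standardised one (observed over expected events), each with a 95% confidence interval;
- a note that these ratios describe the risk in users and are not a causal effect of the drug.

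Keep the propensity-adjusted negative binomial and Cox models on the full population beside this table, described as adjusted treated-versus-untreated comparisons and not as comparisons with background.

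The cost is a sentence or two in each section and one more table per report, from data already extracted. The drawback is that the crude or standardised ratio may look less favourable to Bronchitol if users are sicker, which is why the note must go with it.
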